**Rationale:**

The protocol was amended following comments received by the Paul-Ehrlich-Institute (German Competent Authority, PEI) on 23 June 2015 and the MD Anderson Cancer Center Centralized Review Committee (MDACC CRC) on 16 June 2015 and agreed to by Amgen. In addition, some typographical errors were corrected and clarifications added.

The following changes were implemented as requested by the PEI:

- Inclusion of a reference to a country-specific supplement for Germany (inclusion criterion #3 was changed to restrict the enrollment of refractory AML patients to those with refractory disease after at least 2 failed induction attempts)
- An additional response assessment 4 weeks after the end of a treatment cycle in case of an extended treatment free interval due to insufficient recovery of peripheral blood counts
- A tabulated list of potential adverse events was added to the background section
- The requirement for an emergency room with resuscitation equipment during hospitalization
- The requirement for a patient card to be handed to subjects in the outpatient setting
- Removal of sponsor decision (other than safety related reasons) as reason for permanent discontinuation of individual subjects from treatment or from study.

---

The following changes were implemented as requested by the MDACC CRC:

- Addition of short description of rationale for potential implementation of dose step and clarification on process for estimating MTDs in case of dose step.
- Implementation of an additional dose level review team meeting after 5 subjects have been enrolled in the expansion phase of the study

The following additional corrections and clarifications were added:

- In case a cycle ends early and will not be continued due to an interruption of more than 7 days, the end of infusion bone marrow and biomarker assessments should be done once feasible, e.g., in order to determine treatment response and the appropriate duration of the infusion-free interval.
- Correction of an inconsistency concerning re-start of treatment after interruption due to adverse event
- Time to progression was added to the secondary endpoints and secondary objectives to align with section 10.4.3.2, Efficacy Endpoint Analyses
- Correction of a typographical error in the criteria for permanent treatment discontinuation due to DILI
- Correction in the schedule of assessment footnote on vital sign assessments
- Immunological phenotyping of bone marrow was removed from section 7.5.2 as this will not be done for this study
- Correction of typographical error in Table 12, List of Analytes

**Rationale:**

The protocol was amended following comments received by the FDA on May 12th, 2015 and on May 15th, 2015, and in line with the responses to questions submitted to the IND on May 19th, 2015.

The following changes were implemented as requested by the FDA:

- specific recommendations for infection prophylaxis (neutropenic subjects) as well as description of mitigation measures for cytokine release syndrome and tumor lysis syndrome, and provisions for identifying subjects at high risk of cytokine release syndrome and tumor lysis syndrome were added.
- implementation of possibility for DLRM to introduce steroid pre-treatment for subsequent cohorts in case of observation of cytokine release syndrome
- addition of recommendation for 9 days of hospitalization in first treatment cycle
- DLT criteria were updated as per FDA request
- rolling 6 design was replaced with 3+3 design
- the dose escalation scheme was modified in accordance with FDA requests for slower escalation in the first dose cohorts.
- a waiting period prior to dosing of the next subject was implemented for the first 10 subjects receiving step dosing (if applicable)
- an additional time point for coagulation and hematology safety labs was added (8 h post treatment start in the first cycle and after step if applicable)
- the subject population that should receive pre-treatment with hydroxyurea prior to start of AMG 330 treatment was specified

---

In addition to changes requested by the FDA, the following administrative changes were made:

- change of US study manager
- adverse event CRF was replaced with event CRF following current DES standards
- list of analytes for chemistry and hematology were updated to reflect eCRF contents

The purpose of this Statistical Analysis Plan (SAP) is to provide details of the statistical analyses that have been outlined within Protocol Amendment 9 (for study 20120252, AMG 330 dated 15 February 2021). The scope of this plan includes the interim analysis, primary analysis, and final analysis that will be executed by the Amgen Global Biostatistical Science department unless otherwise specified. PK/PD and biomarker analyses will be provided by Clinical Pharmacology, Modeling and Simulation (CPMS) group and clinical biomarker group in Department of Translational Medicine.

2. Objectives, Endpoints and Hypotheses

2.1 Objectives and Endpoints

Primary Objectives:

- Evaluate the safety and tolerability of AMG 330 in adult subjects with relapsed/refractory AML, MRD+ AML and MDS
- Estimate the maximum tolerated dose (MTD) and/or a biologically active dose [eg, recommended phase 2 dose (RP2D)] of AMG 330 in adult with relapsed/refractory AML, MRD+AML and MDS

Secondary Objectives:

- Evaluate the pharmacokinetics (PK) of AMG 330
- Determine the formation of anti-AMG 330 antibodies
- Evaluate the anti-leukemia activity of AMG 330 by evaluating
 - the number and proportion of subjects who respond to treatment with AMG 330. Response is defined as any of the following: complete remission (CR), CR with incomplete recovery (CRi) or morphologic leukemia-free state (all according to Revised International Working Group [IWG] response criteria) or CR with partial hematologic recovery (CRh).
 - the number and proportion of subjects with MDS who respond to treatment with AMG 330. Response is defined as any of the following: CR or marrow CR (all according to Revised IWG response criteria).
 - the number and proportion of subjects with MRD-positive AML (Group 2) who respond to treatment with AMG 330. Response is defined as conversion from MRD+ status with 0.1% threshold to MRD- status

- the duration of response, event-free survival, time to response, and overall survival

Exploratory Objectives:

- Evaluate the protein, nucleic acid, and cellular biomarkers in blood and / or bone marrow, as applicable [eg, cytokines, lymphocyte subsets, minimal residual disease (MRD – Group 1 only), leukemic stem cells (LSCs)]
- Evaluate effects of genetic variations in and phenotype of cancer genes, including apoptotic markers, on adverse event profile and treatment response
- Evaluate mechanisms of resistance
- Evaluate potential measures of clinical benefit including number of blood products transfused and days of antibiotic treatment of infection
- Evaluate the relationship between AMG 330 exposure and response to treatment
- [REDACTED]
- [REDACTED]
- [REDACTED]
- Explore the additional thresholds of conversions to MRD- status in MRD+ AML subjects as an efficacy measure for AMG 330 treatment

Primary Endpoint:

- Safety: subject incidence and grade of adverse events (AEs) and dose limiting toxicities (DLTs)

Secondary Endpoints:

- Pharmacokinetic parameters: half-life, steady state concentration, volume of distribution and clearance of AMG 330
- Incidence of anti-AMG 330 antibody formation
- Efficacy parameters for R/R AML: response rate (response defined as CR/CRi/morphologic leukemia-free state [per modified IWG criteria] or CRh), duration of response, time to response, event-free survival and overall survival (duration of response, event-free survival, and overall survival will only be measured in the expansion cohort)
- Efficacy parameters for MRD-positive AML: response rate (response defined as conversion from MRD+ status with 0.1% threshold to MRD-), time to response,

relapse-free survival, and overall survival (relapse-free survival and overall survival will only be measured in the expansion cohort)

- Efficacy parameters for MDS: response rate (response defined as CR or marrow complete remission [per International Working Group (IWG) standardized response criteria]), duration of response, time to response, event-free survival and overall survival (duration of response, event-free survival, and overall survival will only be measured in the expansion cohort)

Exploratory Endpoints:

- Depletion of LSCs
- MRD response
- Lymphocyte counts, cluster of differentiation (CD) 33+ monocytes and T cells, as well as T cell activation (including T cell subsets). Other immune subsets may also be examined
- [REDACTED]
- [REDACTED]
- [REDACTED]
- Changes in serum cytokine levels
- Frequency and severity of cytokine release syndrome (CRS) and other AEs following [REDACTED] premedication, and alternative dose step schedules of AMG330
- [REDACTED]

2.2 Hypotheses and/or Estimations

AMG 330 will demonstrate evidence of anti-leukemic activity at a well-tolerated dose in subjects with AML and MDS.

3. Study Overview

3.1 Study Design

This is a first-in-human, open-label, phase 1 sequential dose escalation study. AMG 330 will be evaluated as a continuous intravenous (cIV) infusion in adult subjects with relapsed/refractory (R/R) AML (Group 1), MRD+ AML (Group 2) and MDS (Group 3). The study will be conducted at approximately 17 sites in Germany, the Netherlands, Japan, Canada and the United States.

The dose-escalation cohorts will estimate the MTD/biologically active dose, safety, tolerability, PK, and pharmacodynamics (PD) of AMG 330.

For R/R AML (Group 1), planned dose levels for the dose-escalation cohorts are as follows: 0.5, [REDACTED] and 960 µg/day.

[figure not shown]
Intermediate and/or higher dose level(s) up to 1.6 mg of AMG 330 may be evaluated as necessary to reach MTD. The same dose level may be tested in multiple cohorts, but with different dose steps and/or different cycle lengths.

For MRD+ AML (Group 2), planned target dose levels for the dose-escalation cohorts are as follows: [REDACTED] and 960 µg/day. Each target dose level will be preceded by dose steps. Intermediate dose steps and additional target dose level(s) up to 1.6 mg of AMG 330 may be evaluated as necessary. Escalation can continue until the biologically active dose for MRD+ AML is established. Selected target dose levels, with the exception of the maximal tested dose, that have been deemed safe in subjects with R/R AML (Group 1) could be skipped in Group 2 phase 1a dose escalation cohorts based on available safety, PK, and PD data if recommended by the Dose Level Review Team (DLRT).

For MDS (Group 3), planned target dose levels for dose-escalation cohorts are as follows: [REDACTED] and 960 µg/day. Each target dose will be preceded by dose steps. Intermediate dose steps and additional dose level(s) up to 1.6 mg of AMG 330 may be evaluated as necessary. Escalation can continue until MTD for MDS is established. Selected target dose levels, with the exception of the maximal tested dose, that have been deemed safe in subjects with R/R AML (Group 1) could be skipped in Group 3 phase 1a dose escalation cohorts based on available safety, PK, and PD data if recommended by the DLRT.

It is anticipated that more than one MTD may be estimated, one for each dose step and one for the target dose. Should the initial dose be limited by adverse events related to first dose effects (eg, cytokine release syndrome [CRS]), the second MTD for the target dose will be estimated after giving the initial dose at MTD (dose step). Starting with cohort 6 (R/R AML, Group 1), a dose step in each cycle is mandatory for all newly enrolled subjects. Administration of a prophylactic steroid dose (8 mg IV dexamethasone) within 1 hour prior to the dose step for prevention of cytokine release is mandatory. The additional assessments described in the schedule of assessments for dose steps (in Protocol Table 14) apply.

[REDACTED]

Dose Escalation:

For Group 1 (R/R AML), dose escalation will be conducted in two stages. In the single subject cohorts, single subjects will be enrolled at dose levels anticipated to be lower than those at which adverse events related to AMG 330 will be observed. Once higher dose levels are open for enrollment or drug related safety or efficacy signals are observed, multiple subject cohorts of up to 6 subjects per dose level will open for enrollment (3+3 design). Subjects who complete the DLT period may proceed to a higher dose level for the following treatment cycle if no DLT has been reported for either this subject or any other subject in this dose cohort after completion of the DLT period, and once the next dose cohort is open for enrollment. (see Section 7.2.2 in protocol for details on assessments applicable in case of intra-subject dose escalation).

In Group 1 (R/R AML), should the initial dose be limited by adverse events related to first dose effects (eg, CRS), dose steps will be implemented. An optimal dose step schedule and MTD for the target dose will be estimated following decision rules.

For Groups 2 and 3 (MRD+ AML and MDS), each dose escalation cohort will enroll a minimum of 3 to a maximum of 9 evaluable subjects. Dose escalation will be guided by a modified toxicity probability interval approach (mTPI-2; [Guo et al. 2017](#)). The DLRT will review all available safety, laboratory, PK and PD data and provide dose-finding recommendations.

For Groups 1, 2 and 3, enrollment will occur simultaneously, and each Group will progress from the dose escalation to the dose expansion independently. The total number of subjects to be enrolled for the dose escalation will depend on the toxicities observed as the study progresses. Additional subjects may be required if other dose levels or alternate treatment schedules are explored.

Enrollment in Group 4 is independent from enrollment in Groups 1, 2 and 3. For Group 4, enrollment in Arm 1 will occur first. Once all subjects in Arm 1 have initiated treatment, enrollment into Arm 2 will begin. Once all Group 4 subjects have completed the DLT period, enrollment into Group 5 can commence. If there are 2 arms in Group 5, all subjects in Arm 1 must have initiated treatment before enrollment into Arm 2 can begin.

Expansion Cohorts:

[figure not shown]
At completion of the dose escalation cohorts, additional subjects will be enrolled in dose expansion cohorts to gain further clinical experience, safety and efficacy data in subjects with AMG 330. The dose to be evaluated will be at or below the MTD estimated in the dose escalation cohorts. If there is at least 1 responding subject in the first 10 subjects enrolled in the expansion cohort, additional (up to 20) subjects will be enrolled after evaluating safety, tolerability and anti-leukemia activity of AMG 330 using all available cumulative data. Additional expansion cohorts testing alternative dose levels or biologic subsets may be considered by amendment.

For each Group, a final estimate of the MTD and/or RP2D will be evaluated and confirmed utilizing all DLT-evaluable subjects from the dose escalation and the dose expansion cohorts.

Study Schema:

The overall study design is described by a study schema at the end of the protocol synopsis and below (Figure 1).

Figure 1. Study Design and Treatment Scheme

3.2 Sample Size

It is anticipated that approximately 256 subjects will be enrolled in this study. For the dose escalation cohorts, approximately 70 subjects will be enrolled in Group 1 (R/R AML), up to 36 subjects will be enrolled in Group 2 (MRD+) and up to 36 subjects will be enrolled in Group 3 (MDS). Up to 30 additional subjects will be enrolled in a dose expansion cohort for each group (up to 90 additional subjects total). Approximately 24 subjects will be enrolled in the Groups 4 and 5, 6 subjects for each arm in Group 4 and 6-12 subjects in Group 5.

The sample size in the dose escalation is based on practical considerations and it is consistent with conventional oncology studies with the objective to estimate the MTD. With 3 subjects per cohort, there is a 27-70% probability of observing at least one DLT if the true DLT rate is 10-33% and with 6 subjects per cohort, there is a 47-91% probability.

In the dose expansion cohorts, a subject number of 10 will provide a 65% probability of observing at least one adverse event with 10% incidence rate and 89% probability of observing at least one adverse event with 20% incidence rate.

Assuming a response rate of less than 5% and at least one subject having a response in the first 10 subjects for the enrollment to continue in the expansion cohort, there is greater than 59% chance of stopping the expansion cohort.

Assuming a response rate of greater than 20% and at least one subject having a response in the first 10 subjects for the enrollment to continue in the expansion cohort, there is less than 11% chance of stopping the expansion cohort. A sample of 30 subjects would provide a 96% probability of observing at least one adverse event, when the incidence of the adverse event is 10%. A sample of 30 subjects would provide a 100% probability of observing at least one adverse event, when the incidence of the adverse event is 20%. An exact 80% binomial confidence interval (CI) will be provided for overall response rate. With the 10 subjects and 20% overall response rate, the expected 80% CI would be 5.5% to 45.0% with the half-width 19.8%.

Assuming a sample of 30 subjects and 20% overall response rate, the expected 80% CI would be 10.9% to 32.5% with the half-width 10.8%.

3.3 Adaptive Design

For MRD+ AML (Group 2) and MDS (Group 3), dose exploration will be guided by pre-specified monitoring rules, which is based on a modified toxicity probability interval algorithm (mTPI-2; [Guo et al, 2017](#)) with a target DLT rate of 25% and an acceptable

toxicity probability interval of 20%-30%. Consistent with conventional oncology phase 1 study designs (eg, 3 + 3 design) and given the imprecision with making decisions using as few as 3 subjects, in the instance of 1 DLT in the initial 3 subjects at a dose level then, as appropriate, the design allows expansion at the dose level beyond 3 subjects.

The mTPI-2 algorithm employs a simple beta-binomial Bayesian model. Let p_T be the target toxicity level and $(p_T - \epsilon_1, p_T + \epsilon_2)$ be the equivalence toxicity interval denoted as EI. The unit toxicity interval $(0, 1)$ is divided into subintervals with equal length given by $(\epsilon_1 + \epsilon_2)$. Let the under-dosing intervals (LI) denote for a set of intervals below EI, and the overdosing intervals (HI) for a set of intervals above EI. The 3 types of dosing intervals (EI, LI, HI) are associated with 3 different dose escalation decisions. The LI correspond to a dose escalation (E), the HI correspond to a dose de-escalation (D), and proper dosing intervals (EI) correspond to staying at the current dose (S). This study design uses a target toxicity level, p_T of 25%, and EI of (20%, 30%).

Decision rules are based on the unit probability mass (UPM) calculated on these equal-length intervals. Given an interval and a probability distribution, the UPM of that interval is defined as the probability of the interval divided by the length of the interval. The mTPI-2 design calculates the UPMs for the each of equal-length dosing intervals. If the interval with the largest UPM is from LI, EI or HI, then the corresponding dose decision would be E, S, or D, respectively.

A dose level will be considered unsafe, with no additional subjects enrolled at that dose level, if it has an estimated 95% or more probability of exceeding the target DLT rate p_T (ie, $P [DLT > p_T | \text{data}] > 95\%$) with at least 3 evaluable subjects treated and evaluated at that dose level.

After the escalation phase is completed, final DLT rates at each dose level will be estimated by isotonic regression ([Ji et al, 2010](#)). The MTD will be determined as the dose level with the DLT estimate closest to the target toxicity level of 25%. In the case of dose levels with estimated toxicity of equal distance (tied dose levels) from the target toxicity of 25%, the following approach will be used ([Ji et al, 2010](#)): among all tied dose levels the highest dose level with target toxicity $\leq 25\%$ will be selected, unless all tied

dose levels have estimated toxicity >25%, in which case the lowest dose level will be selected.

mTPI-2 Trial Monitoring Table

Number of DLTs	n=3	n=4	n=5	n=6	n=7	n=8	n=9
0	E	E	E	E	E	E	E
1	S ^a	S	S	E	E	E	E
2	D	D	D	D	S	S	E
3	DU	DU	DU	D	D	D	D
4	.	DU	DU	DU	DU	DU	D
5	.	.	DU	DU	DU	DU	DU
6	.	.	.	DU	DU	DU	DU
7	DU	DU	DU
8	DU	DU
9	DU

DLT = dose-limiting toxicity; E = escalate to the next higher dose level; S = stay at the current dose level; D = de-escalate to the next lower dose level; DU = current dose is unacceptably toxic; mTPI = modified toxicity probability interval.

^a The original mTPI algorithm was "D" for this case and is modified to "S" to collect more information on this dose. The modified decision rule is similar to a 3+3 design.

4. Covariates and Subgroups

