### 3.1.3 Design of Group 3: MDS

The dose-escalation cohorts will estimate the MTD, safety, tolerability, PK, and PD of AMG 330 in subjects with MDS. The following dose escalation cohorts will be evaluated:

[REDACTED]

Selected

**target dose levels, with the exception of the maximal tested dose, that have been deemed safe in subjects with R/R AML (Group 1) could be skipped in Group 3 dose escalation cohorts based on available safety, PK, and PD data if recommended by the DLRT.** Administration of 8 mg IV dexamethasone within 1 hour prior to the dose step for prevention of cytokine release is mandatory. Up to 36 subjects with MDS will be enrolled in the phase 1a dose escalation cohorts; each dose escalation cohort will enroll a minimum of 3 and a maximum of 9 evaluable subjects.

### 3.1.4 Dose Escalation Rules for Groups 2 and 3

For both Group 2 and Group 3, a minimum of 3-4 subjects will be enrolled initially into each cohort and additional subjects up to a maximum of 9 evaluable subjects will be added at the Sponsor's discretion. After all subjects in each dose escalation cohort have either completed the DLT evaluation period or had a DLT, the DLRT will meet to determine whether it is appropriate to escalate or de-escalate the dose, or whether to stop the study for safety concerns. The DLRT will evaluate all available safety, laboratory, PK, and PD data to guide their dose-finding recommendations. **Based on DLRT recommendation, selected target dose levels, with the exception of the maximal tested dose, may be skipped in Groups 2 and 3 dose escalation cohorts if these dose levels have been evaluated in subjects with R/R AML (Group 1) and deemed safe.** [Appendix H](#) shows the mTPI-2 escalation/de-escalation guideline with a

target toxicity probability of 0.25 and an acceptable toxicity probability interval of 0.20 to 0.30. A dose level will be considered unsafe, with no additional subjects enrolled at that dose level, if it has an estimated  $> 95\%$  probability of exceeding the target DLT rate  $p_T$  (ie,  $P [DLT > p_T | \text{data}] > 95\%$ ) with at least 3 subjects treated and evaluated at that dose level. Dose exploration will continue until the current recommended dose cohort reaches at least 6 evaluable subjects or until the highest protocol-defined dose has been evaluated.

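### The SAP's mTPI-2 table says escalate at 2 DLTs in 9 subjects, where the algorithm in the same section says stay

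*SAP*

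**What the plan says.** Dose finding in Groups 2 (MRD+ AML) and 3 (MDS) follows mTPI-2. SAP section 3.3 sets the target DLT rate at 25% and the equivalence interval (EI) at 20% to 30%. On the model it says: "The mTPI-2 algorithm employs a simple beta-binomial Bayesian model". The unit interval "is divided into subintervals with equal length given by" the width of the EI, which is 0.10. The rule is then: "If the interval with the largest UPM is from LI, EI or HI, then the corresponding dose decision would be E, S, or D, respectively". Here UPM is posterior probability divided by interval length, and LI and HI are the intervals below and above the EI. A dose is declared unsafe (DU) when the posterior probability of exceeding 25% passes 95%, "with at least 3 evaluable subjects treated and evaluated at that dose level". Protocol section 6.2.1.4 states the same algorithm.

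The monitoring table in SAP 3.3 is keyed "E = escalate to the next higher dose level; S = stay at the current dose level". Its row for 2 DLTs reads D, D, D, D, S, S, E for n = 3 to 9. The SAP's summary of changes (Appendix C) reprints the same row. One departure from the algorithm is declared, in footnote a, for 1 DLT in 3 subjects (D changed to S), with the comment "The modified decision rule is similar to a 3+3 design".

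Cohorts hold 3 to 9 evaluable subjects. Protocol section 3.1.4 adds: "Dose exploration will continue until the current recommended dose cohort reaches at least 6 evaluable subjects", or until the highest protocol-defined dose has been evaluated.

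**The concern.** Two DLTs in nine is an observed rate of 22.2%, inside the interval that the plan treats as acceptable and 2.8 points below target. An mTPI-2 design with these settings would be expected to stay at such a dose, yet the table says escalate. If the cell is wrong, a pre-specified safety threshold in two of the three dose-finding groups points the less cautious way: new subjects would be recommended for a higher dose when the current one already looks close to target. The DLRT would also hold two different pre-specified answers to the same data, both from one section of the SAP.

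**Working it through.** **Inputs.** From SAP 3.3: target 0.25; EI (0.20, 0.30); interval width 0.10, so LI = (0, 0.1) and (0.1, 0.2), EI = (0.2, 0.3), and HI = (0.3, 0.4) up to (0.9, 1.0); DU if P(p > 0.25 | data) > 0.95 with n ≥ 3. The prior is not stated, so Beta(1,1) is assumed first and then varied.

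**Formulas.** With x DLTs in n subjects the posterior is Beta(1 + x, 1 + n − x). For these integer parameters, P(p ≤ t | data) = P(Binomial(n + 1, t) ≥ x + 1). All intervals have the same width, so the largest UPM is the largest interval probability.

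**Neighbouring cells reproduce.**

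| Data | Posterior | (0.1, 0.2) | (0.2, 0.3) EI | (0.3, 0.4) | Rule | Table |
|---|---|---|---|---|---|---|
| 1/6 | Beta(2,6) | 0.274 | 0.247 | 0.171 | E | E |
| 2/6 | Beta(3,5) | 0.122 | 0.205 | 0.227 | D | D |
| 2/8 | Beta(3,7) | 0.209 | 0.275 | 0.231 | S | S |
| 3/9 | Beta(4,7) | 0.108 | 0.230 | 0.267 | D | D |

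**The cell in question, 2/9.** The posterior is Beta(3,8), so P(p ≤ t) = P(Binomial(10, t) ≥ 3):

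- t = 0.1: 0.0702
- t = 0.2: 0.3222
- t = 0.3: 0.6172
- t = 0.4: 0.8327

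The interval probabilities are:

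- (0.1, 0.2): 0.3222 − 0.0702 = 0.2520, UPM 2.52
- (0.2, 0.3), the EI: 0.6172 − 0.3222 = 0.2950, UPM 2.95
- (0.3, 0.4): 0.8327 − 0.6172 = 0.2155, UPM 2.155

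The EI has the largest UPM, so the rule gives S. The table prints E. The posterior probability that the rate exceeds 25% is P(Binomial(10, 0.25) ≤ 2) = 0.526.

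**Whole table.** Of the 49 cells with x ≤ n, 47 match. The mismatches are 1/3 (rule D, table S, covered by footnote a) and 2/9 (rule S, table E, no footnote).

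**Where E would begin.** At 2/10 the EI still leads, 0.305 against 0.293 for (0.1, 0.2), giving S. At 2/11 the order reverses, 0.331 for (0.1, 0.2) against 0.305 for the EI, giving E. The first E for 2 DLTs is therefore at n = 11, beyond the cohort maximum of 9.

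**Other priors.** A search over 900 Beta(a, b) priors (a and b from 0.1 to 3.0 in steps of 0.1), leaving 1/3 aside, found none that reproduces the table. Four, including Beta(1,1), leave a single mismatch, and each time it is 2/9. A Jeffreys prior does give E at 2/9, but it turns 1/4 and 1/5 into E and 4/8 into D, all against the table. It also gives S at 1/3, where footnote a says the unmodified result was D. The older three-interval mTPI gives S at 2/9 as well.

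**How often the cell would arise.** For a cohort of exactly 9, P(2 DLTs) = 36 p²(1 − p)⁷:

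| True DLT rate | P(exactly 2 in 9) |
|---|---|
| 20% | 0.302 |
| 25% | 0.300 |
| 30% | 0.267 |
| 35% | 0.216 |

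**The case against.** The case for leaving this alone concedes the arithmetic and goes to consequence.

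- **The table is advisory.** The DLRT recommends doses from all safety, laboratory, PK and PD data, including grade 3 or higher events that are not DLTs. This stands: an E obliges nobody to escalate.
- **The protocol's operating chart is Appendix H.** Its table is not in the text available for review, so the slip may be confined to the SAP. This also stands, although SAP 7.1 refers dosing recommendations for these groups to section 3.3, which holds both the rule and the table.
- **Reaching n = 9 is not automatic.** Column n = 6 contains no S, so a dose filled in threes that follows the table leaves at 6. Getting to 2/9 needs other increments (for example 4, then 8 with S at 2/8, then 9), extra subjects at the sponsor's discretion, or a return to the dose after de-escalation. The binomial figures above are conditional on n = 9 and do not give the overall frequency of the cell.
- **Later safeguards remain.** A higher dose has its own D and DU rules, the MTD comes from isotonic regression, and a DLT rate of 33% or more at the MTD or RP2D can suspend expansion enrolment.
- **The prior is inferred and the margin is modest** (UPM 2.95 against 2.52). True, but no prior tried makes the printed table consistent.

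One could also argue that S has no meaning in a full cohort. It does: under Protocol 3.1.4 a recommended dose with at least 6 evaluable subjects meets the condition for ending exploration. If E was chosen because the cohort is full, that is a second departure from the algorithm and should be declared like the first.

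**Conclusion.** The concern holds. The 2/9 cell contradicts the rule stated in the same section, and nothing in the SAP or protocol declares it deliberate. Its repetition in the summary of changes makes a text-extraction error unlikely. The defect is one cell, but it is a pre-specified escalation threshold in a first-in-human trial, and it errs in the less cautious direction at a dose with slightly better than even posterior odds (0.53) of exceeding the target rate. The conclusion rests on a Beta(1,1) prior, which reproduces every other cell that is not footnoted. Practical impact is limited by DLRT discretion and by how often a cohort reaches 9, and it depends partly on whether Appendix H carries the same cell. None of these resolves the contradiction.

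**What to change.** Regenerate the table from the stated algorithm, which changes the entry for 2 DLTs at n = 9 from E to S. If E is intended, add a footnote declaring it a second deliberate departure and giving the reason. State the prior in SAP 3.3 so that the table can be reproduced. Check Protocol Appendix H and make the two tables identical. The cost is one SAP table cell and a sentence on the prior, plus the same cell in Appendix H if it appears there. No design change or new data are needed.
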